Females of childbearing potential should use reliable methods of contraception from the time of screening until 6 months after discontinuing study treatment. Acceptable methods of contraception include abstinence, tubal ligation, combined oral, transdermal, or intra-vaginal hormonal contraceptives, medroxyprogesterone injections (e.g., Depo-Provera), copper-banded intra-uterine devices, hormone impregnated intra-uterine systems and vasectomised partners. All methods of contraception (except for total abstinence) should be used in combination with the use of a condom by their male sexual partner for intercourse.

Males

Male patients must use a condom during sexual intercourse with all sexual partners including a pregnant female partner during the study and for 4 weeks after discontinuing study treatment. However, where a sexual partner of a male participant is a woman of childbearing potential who is not using effective contraception, men must use a condom during sexual intercourse during the; study and for 6 months after discontinuing study treatment. Male patients should avoid procreation during the trial and for 6 months after discontinuing study treatment.

C. Risks of Harm to Non-Participants

When evaluating the patient during the visit, research personnel will wear appropriate personal protective equipment (PPE) as recommended by the CDC. This includes the following:

- Gown
- Gloves
- Eye/face protection (i.e., goggles, face shield)
- If available, National Institute for Occupational Safety and Health (NIOSH)-certified disposable N95 or better respirator. The CDC has stated that surgical (face) masks have been determined to be an acceptable alternative to N95 or better respirators, when the supply chain of respirators cannot meet the demand so long as procedures that are likely to generate respiratory aerosols are not being performed. The use of mid-turbinate nasal swabs to collect viral load specimens during this study is not considered an aerosolizing procedure.

D. Assessment of Social Behavior Considerations N/A

E. Minimizing Risks of Harm

Once participants are started on study drug, monitoring for prolongation of QTc or development of polymorphic ventricular tachycardia is required. The Zio AT (iRhythm Technologies, Inc.) is a mobile cardiac telemetry device that allows continuous monitoring of the QTc interval and heart rhythm abnormalities. The Zio AT consists of a small transdermal patch that is applied on the participant's upper chest and a gateway device (size of a cell phone) that has to be kept within 10 feet of the participant. The ECG signal is transmitted to iRhythm technologies via the internet using the gateway. The participant does not have to change batteries or do anything to the device for the 10-day monitoring interval. We have used this device clinically and participant compliance is excellent. The rhythm is monitored continuously for arrhythmias and our EP-cardiology team will be notified immediately for any run of ventricular tachycardia (VT) greater than 4 complexes and other significant arrhythmias (pauses greater than 3 seconds, heart block, atrial fibrillation). We are monitoring for any run of VT since we have found that most episodes of torsade de pointes VT are preceded by shorter runs of polymorphic VT. The participant can also

trigger a transmission by pressing a small button on the transdermal patch if they experience any cardiac symptoms. We will monitor the QTc with this device. We will obtain a baseline transmission at the initial visit after the participant has been deemed to be eligible based on the Kardia Mobile 6L QTc measurement. We will ask the participant to do a transmission for QTc measurement 2 hours after the first dose of study drug. These will be reviewed and QTc measured by our EP cardiology team. We will then monitor the QTc interval twice a day at two predetermined times. This type of monitoring is equivalent to what can be done in the hospital on telemetry and in practice may be superior since the protocol will be strictly adhered to and measurements made by an electrophysiologist. If QT interval increases from baseline of > 60msec or QT > 500 msec, the medications, if still being taken, will discontinued at that time. Participant QT will be monitored every 6 hours until the interval returns to baseline. If a serous arrhythmia is detected during the continuous monitoring, the study cardiologist and participant will be promptly contacted, and the participant will be directed to seek medical treatment as appropriate.

Hemolytic anemia has been associated with long-term use of ribavirin. The study participants will receive only a 5 day course of medication. As an added safety measure hemoglobin level will be checked at baseline, day 14 and then again at day 28. A comprehensive metabolic panel will be drawn at baseline, day 14, and day 28.

 Certificate of Confidentiality N/A

Provisions to Protect the Privacy Interests of Participants

Every effort will be made to maintain patient confidentiality. Research and hospital records are confidential. Patient's name or any other personally identifying information will not be used in reports or publications resulting from this study. The Food and Drug Administration or other authorized agencies (e.g., qualified monitors from Rutgers), may review patients records and as required.

Patients will be required to sign a HIPAA authorization, providing permission to use identifiable health information to be used and/or disclosed for research purposes. Provisions for protecting the privacy interests of include:

- Ensuring that the conditions under which a procedure is performed, or information is collected (e.g., physical locations, telephone contact, mail, or email solicitations) afford protections against interactions with participants being witnessed, overheard or inadvertently intercepted or viewed.
- Limiting the information being collected to only the minimum amount of data necessary to accomplish the research purposes.

The research team will make all efforts to ensure confidentiality is maintained by:

- Protecting PHI against public viewing;
- Proper storage and disposal of documents that contain PHI;
- Safeguarding computer workstations and databases that access PHI.

F. Potential Benefits to Participants

There may be direct benefit to the patient for participation in this study because the study participant may receive hydroxychloroquine sulfate ribavirin and nitazoxanide, which are FDA approved and have been shown to have potential activity in patients with COVID-19, although this does not guarantee that each individual participant will benefit.

Data gathered from this study may allow us to identify an effective treatment for COVID-19 that could result in benefit to the patient or society as a whole in the future.

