- Obtain urine pregnancy test for females of childbearing potential
- Collect research specimens: mid-turbinate nasal swab and blood for CBC, chem profile and immune status
- Randomize study participant
- Dispense study medication
- Provide Zio AT ECG monitoring device for ongoing Q-T interval assessment
- Provide thermometer and pulse oximeter and home collection kits and provide education on use
- Provide education to participant on how to complete temperature log and confirm medication self-dosing and self-collection of mid-turbinate swab.
- Study participant doses self with prescribed study medications the same day if instructed by the study staff

• Days 1-5 – Treatment Period (phone /online)

- Study participant doses self with prescribed study medications days 1 to 5
- Self-collecting of mid-turbinate swab day 3
- Questionnaire completed by participant daily day 1-day 5
- Temperature, PO2, and pulse
- o Day 3 telephone call procedure review and confirm self- specimen collection/AEs
- Days 6- 10
 - Questionnaire completed by participant days 6 to10
 - Self-collecting of mid-turbinate swab days 6 and 10
 - Temperature, PO2 and pulse
 - Day 6 and 10 telephone call procedure review and confirm self-specimen collection/AEs
- Day 14- Follow-up (in person)
 - In person visit to draw blood sample for CBC and chem panel
 - o Return Zio AT ECG monitoring device
- Day 28 Follow-up (in person)
 - In person visit to draw blood sample for CBC, chem panel, and immune function at 28 days
 - Obtain urine pregnancy test for females of childbearing potential
 - o Questionnaire completed by participant
 - o Final AE assessment

Study Flow/Schedule of Events:

Procedure	Pre- Screen -5 days	Screening /Baseline (Day 0/1)	Daily x 5 days	Days 6 to 10	Days 3, 6, 10	Day 14 (Office)	Day 28 +/- 4 (Office)
Pre-screen questionnaire	Х						
Consent		Х					
Baseline questionnaire (inc. Medical History)		X					
Q-T Interval		Х	Х	Х			
Self administered Symptom questionnaire		Х	Х	X			Х
Drug accountability (Treatment compliance)		Х	Х				X
Temperature		Х	Х	х			
PO2 and Pulse		Х	Х	х			
Urine Pregnancy Test		Х					Х
CBC w/ diff/platelet		Х				Х	Х
Comprehensive metabolic panel		Х				Х	Х
Mid-turbinate self nasal swab for viral shedding		Х			Х		
Blood test for immune function		X					Х
Study medication		X (if day1)	X (BID)				
Telephone Follow-up procedure review & confirm self- specimen collection/					X		
AE Review					х		x

- 2. Treatment Plan:
 - Dosage and Administration

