 - Arm 1: NTZ 1000 mg (2 x 250 mg tablets BID for day one) and then 1000 mg (2 x 250 mg tablets BID for 4 days) RBV 1200 mg (3 x 200 mg capsules BID day one) and then RBV 800 mg (2 x 200mg capsules BID for 4 days) HCQ 800 mg (2 x 200 mg tablets bid day one) and then HCQ 400 mg (1 x 200 mg tablet BID for 4 days)
 - Arm 2: Placebo for NTZ (2 tablets BID for day one and then 2 tablets BID for 4 days) Placebo for RBV (3 capsules BID day one and then 2 capsules BID for 4 days) Placebo for HCQ (2 tablets bid day one and then 1 tablet BID for 4 days)

Hydroxychloroquine sulfate (HCQ)

One hydroxychloroquine sulfate tablet contains 200 mg of hydroxychloroquine sulfate, which is the equivalent to 155 mg base.

Ribavirin (RBV)

One ribavirin capsule contains 200 mg of ribavirin.

Nitazoxanide (NTZ)

One nitazoxanide tablet contains 500 mg of nitazoxanide.

Take all tablets/capsules with a meal or a glass of milk.

All study drugs should be stored at room temperature 20°-25° (68°-77 °F).

Concomitant Medications & Supportive Guidelines

Study participants can receive full supportive care therapies concomitantly during the study. We will advise rest, fluids, hot/ showers/baths. We will recommend NO antipyretics since they make infections worse by interfering with the generation of fever--which is considered beneficial until it reaches 102 degrees F.

B. Participant Enrollment

We will identify asymptomatic or mildly symptomatic participants who test positive for SARS-CoV-2 from the Rutgers Coronavirus Cohort (RCC) and hospital screening programs, or from the community through advertisements at our medical center, university, and in local publications. The recruiting materials will direct the potential participants to online materials that include information about the trial, consent forms, and a screener questionnaire to assess eligibility. If eligible for the trial, we will answer any questions and provide as much time as needed to review all study materials. The participant may then electronically sign the consent or, as an alternative, wait until the initial visit to re-review and sign the consent. The consenting process will be primarily performed remotely to protect research personnel.

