As soon as possible after consent, the participant will participate in an in person visit for baseline biospecimen collection. On arrival, research staff wearing PPE will re-review the consent, confirm/obtain signatures, measure the PO2, do a urine pregnancy test in women with potential to be pregnant and measure the baseline QTc interval with the Kardia Mobile 6L (AliveCor, Inc). A 6 lead EKG is obtained when the patient places their fingers on 2 electrode sensors while holding

the device on their leg. The ECG is uploaded to an iPhone and the tracing is sent to the Electrophysiologist cardiologist who will calculate the QT and QTc. The device is approved by the FDA for QTc measurements. The participant will be excluded if the Q-T interval is prolonged beyond 450 Msec. We will also exclude anyone who has a PO2<92% or a positive pregnancy test. We will randomly allocate the participant, provide the assigned medications, and obtain mid-turbinate self nasal swab and blood samples. We will also take the participant's temperature and pulse. We will provide education to the patient on how to complete all at-home study procedures and use all ancillary study supplies which we will provide (self nasal swab specimen kits, thermometer, and pulse oximeter).

We will telephone the participant about 2 hours after the initial medication dose to confirm that the Zio AT patch has been triggered for the one-time 2 hour reading (see the Risks of Harm/Potential for Benefits to Subjects to Subjects section, page 35), review the BID dosing schedule, study procedures, and any participant questions. We will also call on days 3, 6, and 10 for procedure review and to confirm self- specimen collection and AE review. We will have an in person visit on day 14 to collect a blood specimen and on day 28 to collect a blood specimen and urine pregnancy test, review medical status and AEs Self collection of mid-turbinate nasal swab to measure viral shedding will be on days 3, 6 and10 post randomization.

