Availability: FDA approved; commercially available hydroxychloroquine sulfate will be supplied free of charge to all patients enrolled.

[figure not shown]
Generic name: Ribavirin Commercial name:

For complete information please refer to the package inserts at http://dailymed.nlm.nih.gov/dailymed/ribavirin

Chemical name: 1-β-Dribofuranosyl-1H-1,2,4-triazole-3-carboxamide

Source: Commercially available

 $C_8 H_{12} N_4 O_5$ and the molecular weight is 244.2

Ribavirin, USP is white, crystalline powder. It is freely soluble in water and slightly soluble in dehydrated alcohol. Each film-coated ribavirin tablet intended for oral administration contains 200 mg or 400 mg or 500 mg or 600 mg of ribavirin. In addition, each tablet contains the following inactive ingredients: crospovidone, hypromellose, iron oxide red, iron oxide yellow, magnesium stearate, microcrystalline cellulose, polyethylene glycol, povidone, silicon dioxide, talc, and titanium dioxide.

Pharmacokinetics

Multiple dose ribavirin pharmacokinetic data are available for HCV patients who received ribavirin in combination with peginterferon alfa-2a. Following administration of 1200 mg/day with food for 12 weeks mean±SD (n=39; body weight greater than 75 kg) AUC was 25,361±7110 ng·hr/mL and C was 2748±818 ng/mL. The average time to reach C was 2 hours. Trough ribavirin plasma concentrations following 12 weeks of dosing with food were 1662±545 ng/mL in HCV infected patients who received 800 mg/day (n=89), and 2112±810 ng/mL in patients who received 1200 mg/day (n=75; body weight greater than 75 kg). The terminal half-life of ribavirin following administration of a single oral dose of ribavirin is about 120 to 170 hours. The total apparent clearance following administration of a single oral dose of ribavirin is about 26 L/h. There is extensive accumulation of ribavirin after multiple dosing (twice daily) such that the C at steady state was four-fold higher than that of a single dose.

Contraindications:

Ribavirin

Pregnancy: Women who are or may become pregnant. Ribavirin may cause fetal harm when administered to a pregnant woman. women who are or may become pregnant. If this drug is used during pregnancy, or if the patient becomes pregnant while taking this drug, the patient should be apprised of the potential hazard to the fetus Men whose female partners are pregnant.

Hemoglobinopathies: Patients with hemoglobinopathies (e.g., thalassemia major or sickle-cell anemia).

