The participant will then come to the study location at [name] to complete final screening for the trial eligibility. P02 will be measured and 6 lead portable electrocardiogram will be performed; if PO2<92% or QT interval is QTc interval > 450 mSEC the participant will be excluded. Females of childbearing potential will have a urine test to confirm that they are not pregnant.

Inclusion Criteria

- 1. Documented SARS-CoV-2 infection by qPCR assay without symptoms or with mild symptoms consistent with COVID-19 performed within the past 7 days
- 2. Age ≥21

Exclusion Criteria

- 1. COVID-19 symptoms requiring hospitalization
- 2. PO2 < 92%
- 3. Short of breath at time of enrollment
- 4. Retinal eye disease
- 5. Known glucose-6 phosphate dehydrogenase (G-6-PD) deficiency
- 6. Known chronic kidney disease, stage 5 or receiving dialysis
- 7. Current use of:
 - Class 3 AAD (amiodarone, dronaderone, dofetilide, sotalol)
 - Class 1A AAD (procainamide, quinidine, disopyramide)
 - Flecainide
 - SSRI: citalopram (Celexa), Escitalopram (Lexapro)
 - chlorpromazine
 - Cilostazol (Pletal)
 - Donepezil (Aricept)
 - Droperidol
 - Fluoconazole
 - Methadone
 - Ondansetron (Zofran)
 - Thioridazine
 - Macrolides (clarithromycin, erythromycin)
 - Fluroquinolones (ciprofloxacin, levofloxacin, moxifloxacin)
 - Tamoxifen citrate
- 8. Pregnancy or women who are breast feeding
- 9. Inability to tolerate oral medications
- 10. Allergy or prior adverse reaction to either hydroxychloroquine sulfate, ribavirin, or nitazoxanide
- 11. Allergy to adhesives
- 12. QTc interval > 450 mSEC for men and women
- 13. History of Torsade de Pointes VT or prior cardiac arrest or congenital long QT interval
- 14. Non-English-speaking

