Cardiovascular side effects have included tachycardia, syncope, and hypertension.

Hematologic

Hematologic side effects have included anemia and leukocytosis.

Renal

Renal side effects have included kidney pain.

B. Procedures which Risk Harm to Embryo, Fetus, and/or Pregnant Participants Women who are pregnant or unwilling to stop breast feeding are excluded from this trial due to the absence of data which demonstrates that this therapy changes morbidity or mortality.

The US FDA labelling for hydroxychloroquine sulcate risk states the following: Teratogenic Effects: Human pregnancies resulting in live births have been reported in the literature and no increase in the rate of birth defects has been demonstrated. Embryonic deaths and malformations of anophthalmia and microphthalmia in the offspring have been reported when pregnant rats received large doses of chloroquine.

Nursing Mothers: Caution should be exercised when administering PLAQUENIL to nursing women. It has been demonstrated that hydroxychloroquine administered to nursing women is excreted in human milk and it is known that infants are extremely sensitive to the toxic effects of 4-aminoquinolines."

The US FDA Labelling for ribavirin states the following: may cause birth defects and/or death of the exposed fetus. Ribavirin has demonstrated significant teratogenic and/or embryocidal effects in all animal species in which adequate studies have been conducted. These effects occurred at doses as low as one twentieth of the recommended human dose of Ribavirin. Ribavirin therapy should not be started unless a report of a negative pregnancy test has been obtained immediately prior to planned initiation of therapy. Extreme care must be taken to avoid pregnancy in female patients and in female partners of male patients.

All patients must be made fully aware of the information relating to the potential for reproductive toxicity as detailed in the Informed Consent Form. Patients of childbearing potential and their

partners, who are sexually active, must agree to the use of two highly effective forms of contraception throughout their participation in the study and for 6 months after last dose of study drug(s).

Women of childbearing potential

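### Men with a pregnant partner are contraindicated for ribavirin in Section 1.7, but no eligibility criterion excludes them and no stated screening step asks about a partner's pregnancy

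*Combined protocol and SAP*

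**What the plan says.** **Contraindication.** Section 1.7, under the ribavirin contraindications, has a pregnancy entry in two parts. The first covers women who are or may become pregnant. The second is "Men whose female partners are pregnant". Contraindications specific to ribavirin with peginterferon follow under a separate lead-in, so this entry is not conditional on interferon.

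**Eligibility.** In Section 4.1 C the only pregnancy-related exclusion is number 8: "Pregnancy or women who are breast feeding". The two inclusion criteria concern the qPCR result and age.

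**Screening.** Section 4.1 C states that "Females of childbearing potential will have a urine test to confirm that they are not pregnant". The baseline procedures in Section 1.3 A say "Obtain urine pregnancy test for females of childbearing potential". Section 1.3 B has staff "do a urine pregnancy test in women with potential to be pregnant" and exclude anyone who tests positive.

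**Conduct.** Section 4.7 B, under the rules for males, says "Male patients must use a condom during sexual intercourse with all sexual partners including a pregnant female partner during the study and for 4 weeks" beyond the end of study treatment. The same section reports that ribavirin "may cause birth defects and/or death of the exposed fetus".

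**The concern.** The protocol names two groups that pregnancy should keep away from ribavirin, and its eligibility criteria exclude only one of them. A site following Section 4.1 C as written could randomise a man whose partner is pregnant, and nothing in the visible plan would flag him.

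The fetus is at stake. The protocol treats exposure through the male partner as a real concern: Sections 4.7 A and 4.7 B call for extreme care to avoid pregnancy in female partners of male patients. Section 4.7 B also reports animal effects at one twentieth of the recommended human dose. On the other side of the balance, participants have no symptoms or mild ones, and Section 1.4 says the triple combination has not been used in humans before. Section 4.7 B excludes pregnant women because no data show that the therapy changes morbidity or mortality. That argument applies equally when the pregnancy is the partner's.

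**Working it through.** The check is mainly a comparison of sections; the plan gives no figure of its own to reproduce.

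**1. Contraindication against eligibility criteria**

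| Group in the Section 1.7 pregnancy entry | Covered in Section 4.1 C? |
|---|---|
| Women who are or may become pregnant | Current pregnancy: yes, exclusion 8 and urine test |
| Men with a pregnant partner | No |

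Criteria read: 2 inclusion + 14 exclusion = 16. Criteria that concern a partner's pregnancy: 0 of 16.

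**2. Pregnancy checks before randomisation**

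The check is described in three places: Section 1.3 A (baseline visit list), Section 1.3 B (enrolment) and Section 4.1 C (screening). All three describe the same urine test in female participants. The other history items at baseline are medical history, medication history and symptoms, and no partner item is stated. The contents of the online screening questionnaire are not given. It serves the Section 4.1 C criteria, however, and those would not make a man ineligible even if he reported a pregnant partner.

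**3. What the condom rule does**

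It applies during the study and for 4 weeks after treatment. It is not limited to pregnancies found after enrolment, so its natural reading is that men with pregnant partners may be in the trial. No sentence says outright that they are eligible; the defect is that nothing excludes them.

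**4. Exposure of a man enrolled in this way**

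- Chance of ribavirin, from 35 participants per arm of 70 in total (Section 1.5): 35/70 = 0.5.
- Dose from the treatment plan in Section 1.3 A, "RBV 1200 mg (3 x 200 mg capsules BID day one"), then 800 mg daily for 4 days: 1,200 + 4 × 800 = 4,400 mg.

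These numbers describe exposure to the drug. They do not measure fetal risk, for which the documents give no estimate by this route.

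**The case against.** The strongest reply is that the case was foreseen and given a control. Section 4.7 B names the pregnant partner, requires a condom, and says all patients must be told of the reproductive risk through the consent form. The course lasts five days, and the documents offer no data on fetal exposure through a male partner after so short a course. Much of the ribavirin material in Section 1.7 comes from use with peginterferon in hepatitis C. The questionnaire items are not shown and the consent pages are not available for review, so someone may in practice ask the question. An investigator could also act on Section 1.7 directly.

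Part of this stands. The visible text cannot show that nobody asks, only that no step is stated. The condom rule does reduce exposure, and the residual risk cannot be quantified.

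It does not remove the conflict. The listed contraindication has no exception for short courses or condom use, and the protocol gives no reason for making one. The condom rule depends on unsupervised adherence, with no stated step to identify the men it concerns, and neither the man nor the masked staff would know whether he was taking ribavirin. An investigator wishing to apply Section 1.7 would find Section 4.7 B pointing the other way.

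It is also fair to note that the same contraindication list names hemoglobinopathies, which Section 4.1 C omits too. That widens the problem and does not excuse this instance.

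**Conclusion.** The concern holds. The protocol contraindicates ribavirin in men with pregnant partners, yet following its eligibility criteria as written admits them, with a 1 in 2 chance of receiving the drug. Section 4.7 B mitigates the exposure but neither reconciles the two sections nor justifies the departure.

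This is a participant-safety and eligibility inconsistency that should be corrected. It has no bearing on sample size or on the primary analysis. The number of men affected is unknown and may be small. The finding rests on the visible text: a partner question could exist in the questionnaire or consent form, but no stated criterion would turn the answer into an exclusion.

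**What to change.** 1. Add to the exclusion criteria in Section 4.1 C: men whose female partner is pregnant.
2. Ask male volunteers about this in the online pre-screen and again at the baseline visit, before randomisation, and list the item in Section 1.3 A.
3. In Section 4.7 B, limit the condom rule for a pregnant partner to a pregnancy discovered after enrolment, and say whether study drug stops if dosing is still under way.

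If the sponsor prefers to keep these men eligible, the protocol should say so and justify the departure from Section 1.7. Exclusion is the simpler course. While amending, the rest of the ribavirin contraindication list should be compared with Section 4.1 C.

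The cost is amendment wording, one self-reported question asked twice, and a very slightly narrower eligible population. There are no extra visits or tests.
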